8.8.2 DNA Research

DNA studies will be conducted to analyze the tumor microenvironment with the aim of gain insights into the activation of the immune response and identify possible biomarkers related to the

efficacy of BO-112. The samples may also be used to confirm findings by application of alternative technologies.

8.9 Health Economics OR Medical Resource Utilisation and Health Economics

Health Economics/Medical Resource Utilisation and Health Economics parameters are not evaluated in this study.

9.0 STATISTICAL CONSIDERATIONS

9.1 Statistical Hypotheses and Sample Size Determination

Approximately 80 subjects will be screened to achieve a total of 69 evaluable subjects. For both Cohort A (CRC) and Cohort B (GC/GEJ), subjects must have MSS (pMMR) disease to be considered evaluable for efficacy. This will be determined during the study and therefore subjects with MSI (dMMR) disease will be replaced. Given the low incidence of dMMR in stage IV CRC and in GC/GEJ, it is expected that this number will be low, ie, approximately 1 to 2 subjects to be replaced per cohort. Subjects with dMMR disease will be included in the safety analysis set.

The sample sizes of the cohorts were determined using Simon's 2-stage design ³⁹ to enable a first evaluation of the treatment's activity on tumour response. The designs are based on a one-sided $\alpha = 0.05$; a power 80% and response probabilities based on RECIST 1.1 noted below.

When the prespecified number of subjects for Stage 1 have been enroled and have reached the first on-study response assessment, an interim review of available data will be done by a DMC per cohort. The DMC will take the number of responses defined by the Simon's 2-stage design into consideration together with the ORR, DCR, number of subjects with Grade 3 to 5 AEs, SAEs, and individual subject tumour burden profiles to make a reasoned recommendation to the Sponsor regarding extension of each cohort to the foreseen total number of subjects. The stopping rules for futility based on the observed number of responses are considered nonbinding, leaving the final recommendation for stopping the study after Stage 1 at the discretion of the DMC members.

** The baseline biopsy sample will be evaluated for pMMR (as proxy of MSS) versus dMMR (as proxy of MSI-H) status in Cohort B and subjects who are MSI-H/dMMR will be replaced to ensure the appropriate number of pMMR subjects for the statistical analysis. Data from subjects with dMMR GC/GEJ will be evaluated as part of the safety population for safety parameters, but separately and descriptively for efficacy endpoints. The baseline biopsy sample will be evaluated for PD-L1 status in Cohort B; however, there will be no replacement of subjects based on this since the ORR reported the PD-L1 positive subgroup is 15.5% and for the PD-L1 negative subgroup is 6.4% ⁹.

9.2 Populations for Analyses

For purposes of analysis, the analysis sets in [Table 7](#) are defined.

Table 7 Analysis Sets

Analysis Set	Description
Entered Analysis Set	All subjects who sign the informed consent form.
Full Analysis Set	All enroled subjects who receive at least 1 dose of study treatment (BO-112 or pembrolizumab). pMMR and dMMR subjects will be evaluated separately for efficacy endpoints. dMMR subjects will only be analysed descriptively for efficacy endpoints.
Safety Analysis Set	All enroled subjects who receive at least 1 dose of study treatment (BO-112 or pembrolizumab), i.e. same population as FAS. dMMR subjects will be evaluated together with pMMR subjects for safety endpoints.

9.3 Statistical Analyses

The Statistical Analysis Plan (SAP) will be developed and finalised before interim database lock and will describe the subject analysis sets to be included in the analyses, and procedures for accounting for missing, unused, and spurious data. This section is a summary of the planned statistical analyses of the primary and secondary endpoints.

All analyses, summaries, and listings will be performed using SAS® software (version 9.4 or higher).

The following descriptive statistics will be used as applicable to summarise the study data unless otherwise specified:

- Continuous variables: sample size (n), mean, standard deviation (SD), median, minimum (min), and maximum (max).
- Categorical variables: frequencies and percentages.

Individual subject data will be presented in listings.

9.3.1 Efficacy Analyses

Analyses of efficacy will be conducted separately for each cohort based on all subjects included in the Full Analysis Set. In Cohort A, subjects who are dMMR will be evaluated separately and descriptively only. See [Table 8](#) below.

Table 8 Efficacy Analyses

Endpoint	Statistical Analysis Methods
Primary	Objective Response Rate based on RECIST 1.1 is defined as the percentage of subjects with CR or PR as BOR according to RECIST 1.1. The number and percentage of responders, subjects with CR or PR as BOR, and of non-responders subjects with SD, PD or NE as BOR, will be provided along with 95% CI for ORR. In addition, number and percentage of subjects with CR, PR, SD, PD and non-evaluable (NE) as BOR according to RECIST 1.1 will be provided.
Secondary	
Disease Control Rate (DCR) based on RECIST 1.1 is defined as the percentage of subjects with CR or PR, and the percentage of subjects with SD of at least 12 weeks duration, as BOR according to RECIST 1.1. The number and percentage of subjects achieving disease control, subjects with CR or PR or SD as BOR, and not achieving disease control, subjects with PD or NE as BOR, will be provided along with 95% CI for DCR.
 
 • ORR according to RECIST modified for immune-based therapies (iRECIST) is defined as the percentage of subjects with iCR or iPR as best overall response (iBOR) according to iRECIST. The number and percentage of responders, subjects with iCR or iPR as iBOR, and of non-responders, subjects with iSD, iUPD, iCPD or NE as iBOR, will be provided along with 95% CI for ORR. In addition, number and percentage of subjects with iCR, iPR, iSD, iUPD, iCPD and NE as iBOR according to iRECIST will be provided. • DCR according to iRECIST is defined as the percentage of subjects with iCR or iPR or iSD of at least 12 weeks duration as best overall response according to iRECIST. The number and percentage of subject achieving disease control, subjects with iCR or iPR or iSD as iBOR, and not achieving disease control, subjects with iUPD or iCPD or NE as iBOR, will be provided along with 95% CI for DCR.

	
 • DOR according to RECIST 1.1 is defined as the time in months from the date of first documented response (ie, overall response = CR or PR) to the earlier between the date of first documented progression (ie, overall response= PD) and the date of death. DOR will be analysed using Kaplan-Meier method. Kaplan-Meier estimate of median DOR will be provided with the 95% Cis. Kaplan-Meier DOR curve will be plotted. • PFS according to RECIST 1.1 is defined as the time in months from first dose of study treatment (any agent) to first documented radiologic progression or death, whichever occurs first. Subjects without documented radiologic progression or death event will be censored at last evaluable postbaseline tumour assessment. The number and percentage of subjects who were progression-free, who progressed, who died and censored for PFS will be provided. Kaplan-Meier estimate of median PFS will be provided with the 95% Cis. The proportion of subjects who survived progression-free for at least 12 weeks will be provided along with 95% CI. Kaplan-Meier PFS curve will be plotted. • OS is defined as the time in months from first dose of study treatment (any agent) to death. Subjects without documented death event will be censored at the date he/she was last known to be alive. The number and percentage of subjects who died and censored for OS will be provided. Kaplan-Meier estimate of median OS will be provided with the 95% Cis. The proportion of subjects who survived for at least 6 months will be provided along with 95% CI. Kaplan-Meier OS curve will be plotted.
Exploratory	Will be described in the SAP finalised before interim database lock.

Abbreviations: BOR=best overall response; CI=confidence interval; DCR=disease control rate; DOR=duration of overall response; iRECIST= RECIST modified for immune-based therapies; PR=partial response; RECIST= Response evaluation criteria in solid tumours; SD=stable disease; ORR=overall response rate; OS=overall survival.

Note: the prefix “i” denotes immune-related or immune-based.

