Secondary	
 Efficacy: ORR based on the BOR using RECIST 1.1 Safety: number and proportion of subjects with study treatment-related TEAEs with severity \geq Grade 3 (NCI-CTCAE v 5.0) Further characterisation of safety and of clinical activity of the combination as well as determination of systemic exposure of BO-112 Safety: number and proportion of subjects with TEAEs (any grade) Safety: number and proportion of subjects with related TEAEs (any grade) Tolerability: number of study discontinuations due to related TEAE Efficacy: disease control rate (DCR = CR, PR and SD of at least 12 weeks duration) using RECIST 1.1 Efficacy: ORR based on best overall response using RECIST modified for immune-based therapies (iRECIST) Efficacy: DCR = iCR, iPR + iSD of at least 12 weeks duration) using iRECIST Efficacy: duration of response Efficacy: progression-free survival Efficacy: overall survival rate at 6 months Pharmacokinetics: systemic exposure after first BO-112 administration
Exploratory	
 Evaluation of antitumoural and immunological effects in the TME of the injected lesion. Immune cell profile of TME in injected and noninjected lesions Genetic analysis of the TME

Abbreviations: BOR=best overall response; CR= complete response; DCR=disease control rate; iRECIST= RECIST modified for immune-based therapies; IT=intratumoural; NCI-CTCAE=National Cancer Institute-Common terminology criteria for adverse events; ORR=objective response rate; PR= partial response; RECIST= Response evaluation criteria in solid tumours; SD=stable disease; TEAE=treatment-emergent adverse event; TME=tumour microenvironment.

Note: the prefix “i” denotes immune-related or immune-based.

Overall Design:

[figure not shown]
This is an open-label, Phase II, non-comparative, 2-cohort study with a Simon's 2-stage design.

Cohort A: colorectal cancer (CRC)

Cohort B: gastric or gastro-oesophageal junction cancer (GC/GEJ)

Subjects will be enroled in each cohort for Stage 1 of the study up to the predefined sample size and treated according to the treatment schedule. Enrolment will be suspended per cohort and a Data Monitoring Committee (DMC) will review the safety and efficacy data available at the time that the last subject enroled has reached the first on-study response assessment at Week 7 (= Cycle 3). The DMC will make a recommendation to the Sponsor for each cohort regarding expanding to the total foreseen sample size.

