1.3 Schedule of Activities

Table 1 Schedule of Assessments

Treatment Cycle		1		2	3	4	5	6, 8 ... 34	7, 9 ... 35	EOS
Visit	Screening	V1a Baseline	V1b	V2	V3	V4	V5	V6, V8 ... V34 (even numbered visits)	V7, V9 ... V35 (odd numbered visits)	EOS
Day of visit within treatment cycle	Day -28 to Day -1	Day 1	Day 8 ± 2 days	Day 1 ± 2 days	Days 1 ± 2 days	Days 1 ± 2 days	28 days after last treatment ± 3 days			
Study Week		W1	W2	W4	W7	W10	W13	W16, W22 ... W100	W19, W25 ... W103	
Administrative procedures										
Informed consent Form	X									
Inclusion/Exclusion criteria	X									
Demography	X									
Medical history	X									
Safety										
Physical examination ^a	X	X	X	X	X	X	X	X	X	X
Vital signs ^a	X	X	X	X	X	X	X	X	X	X
12-Lead ECG	X	X					X			X
ECOG PS ^a	X	X	X	X	X	X	X	X	X	X
Adverse events ^a		X	X	X	X	X	X	X	X	X
Concomitant medication ^a	X	X	X	X	X	X	X	X	X	X
Coagulation ^b	X	X	X	X	X	X	X	X	X	

Treatment Cycle		1		2	3	4	5	6, 8 ... 34	7, 9 ... 35	EOS
Visit	Screening	V1a Baseline	V1b	V2	V3	V4	V5	V6, V8 ... V34 (even numbered visits)	V7, V9 ... V35 (odd numbered visits)	EOS
Day of visit within treatment cycle	Day -28 to Day -1	Day 1	Day 8 ± 2 days	Day 1 ± 2 days	Days 1 ± 2 days	Days 1 ± 2 days	28 days after last treatment ± 3 days			
Study Week		W1	W2	W4	W7	W10	W13	W16, W22 ... W100	W19, W25 ... W103	
Haematology ^{b, c}	X	X	X	X	X	X	X	X	X	X
Chemistry, CRP ^{b, d}	X	X	X	X	X	X	X	X	X	X
Thyroid function tests ^e		X			X		X		X	X
Pregnancy (for WOBCP only) ^f	X				X		X		X	X
Efficacy										
Tumour Biopsy ^g		X		X						
Tumour burden and response assessment (per RECIST 1.1) ^{h,i}	X				X		X	V7 and V9 then V12, V15, V18, V21, V24, V27, V30, V33		
Pharmacokinetics										
PK blood sample ^j		X								
Study drug administration										
Pembrolizumab		X ^k		X	X	X	X	X	X	
BO-112 ^l	X	X	X	X	X	X	X	X	X	
Abbreviations: AE=adverse events; CRP= C-reactive protein; CT= computed tomography; ECG=electrocardiogram; ECOG PS= Eastern Cooperative Oncology Group Performance Status; EOS=End of Study; PK=Pharmacokinetic; RECIST= response evaluation criteria in solid tumours; SAE=serious adverse events; V=visit; WOBCP=woman of childbearing potential										

Notes:

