The screening period will be from Days -28 to -1, ie, within 4 weeks before the start of the treatment. The screening assessments will be performed according to the Schedule of Assessments (SoA; see Section 1.3). Baseline will be at Week 1.

Study Treatment Period

The study treatment period will comprise 3-week cycles. Treatment and assessment schedules vary somewhat over time and are described in detail in Section 6.0 and section 1.3, respectively. The overall study duration could be extended up to 2 years (ie, Visit 35 plus the end of study [EOS]

visit 28 days after last dose of treatment) depending on the achieved clinical benefit. Individual subject study duration will depend on maintenance of clinical benefit and tolerability and is expected to range from 2 to 12 months, although the study foresees 2 years of treatment.

The study treatment will consist of BO-112 IT injections in combination with IV infusion of pembrolizumab infusions and will be administered in 3-week cycles for both Cohort A and Cohort B subjects.

BO-112 (1 mg) and pembrolizumab (200 mg) will be administered as described in Section 6.1.

Blood samples will be collected for haematology, renal function and hepatic functions tests, C-reactive protein (CRP), and coagulation parameters measurements, prior to any study drug administration at any visit for the first 13 weeks and subsequently every 6 weeks.

Urine pregnancy test will be performed for all women of childbearing potential (WOCBP). If a urine pregnancy test (within 72 hours prior to treatment) is positive or cannot be confirmed as negative, a serum pregnancy test will be required to confirm negative pregnancy.

Tumour biopsies will be performed at baseline (Week 1) prior to first administration of BO-112, on the “to be injected (injected)” lesions and optionally, of a non-hepatic “not to be injected (noninjected)” lesion. On the Week 4, 1 post-treatment biopsy of the injected lesion and if applicable, of the noninjected lesion will be performed.

Physical examinations (full at baseline and brief at subsequent visits), Eastern Oncology Cooperative Group (ECOG) performance status³⁷, AEs, concomitant medications will be evaluated at screening and each visit (ie, at Week 1, Week 2, and Q3W week thereafter) prior to the pembrolizumab treatment.

End of Study

An EOS visit will be performed for all subjects at 4 weeks after last administered study treatment.

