4.4 End of Study Definition

A subject is considered to have completed the study if he/she has

- Completed the full 35 cycles of treatment

or

- Discontinued treatment and study due to confirmed disease progression and has completed the EOS visit.

Therefore, subjects are not considered to have completed if any of the following apply:

- Withdrawal due to AE
- Withdrawal of consent (patient decision to stop)
- Unconfirmed PD
- Lost to follow-up
- Any other reason

The end of the study is defined as the date of the last visit of the last subject in the study or last scheduled procedure shown in the SoA for the last subject in the study globally.

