8.1 Efficacy Assessments

Tumour imaging is strongly preferred to be acquired by CT scan. For the abdomen and pelvis, contrast-enhanced magnetic resonance imaging (MRI) may be used when CT with iodinated contrast is contraindicated, or when mandated by local practice. Magnetic resonance imaging scan is the strongly preferred modality for imaging the brain. The same imaging technique regarding modality, ideally the same scanner, and the use of contrast should be used in a subject throughout the study to optimise the reproducibility of the assessment of existing and new tumour burden and improve the accuracy of the assessment of response or progression based on imaging. Imaging should include the chest, abdomen, and pelvis.

Tumour assessments will be conducted at time points stipulated in the SoA ([Table 1](#)) based on RECIST 1.1. Initial tumour imaging at screening must be performed within 28 days prior to the date of treatment allocation. The site study team must review screening images to confirm the subject has measurable disease per RECIST 1.1. The first on-study imaging assessment should be performed at 6 weeks (42 days \pm 3 days) from the date of start of treatment. Subsequent tumour imaging should be performed every 6 weeks (42 days \pm 3 days) or more frequently if clinically indicated. After 24 weeks (168 days \pm 7 days), subjects who remain on treatment will have imaging performed every 9 weeks (63 days \pm 7 days). Imaging timing should follow calendar days and should not be adjusted for delays in cycle starts. Imaging should continue to be performed until disease progression is identified and confirmed by the investigator (iRECIST), the start of new anticancer treatment, withdrawal of consent, or death, whichever occurs first.

In case of iUPD, a confirmatory CT scan should be done between 4 to 6 weeks after the iUPD scan depending on the clinical status of the subject and extent of progression. If this interval is 6 weeks after iUPD, this coincides with the next scheduled assessment in the first 24 weeks of the study. If disease progression is not confirmed and treatment continues, tumour imaging should resume at the next scheduled timepoint ensuring an interval between imaging of at least 6 weeks.

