Objective response rate based on best overall response (all time points) using RECIST 1.1 will be the primary efficacy endpoint. RECIST 1.1 will be used as the primary measure for assessment of tumour response, date of disease progression, and as a basis for all protocol guidelines related to disease status except for discontinuation of study treatment. Given the interval of 6 weeks between tumour imaging in the first 24 weeks, there is no requirement to confirm objective response within 4 weeks.

The hepatic lesion that is the site of BO-112 IT administration, if measurable must be included as a target lesion to ensure that any direct effect of the injection is recorded. This lesion(s) will be identified as the site of injection and will also be reported separately.

iRECIST is based on the RECIST 1.1 but adapted to account for the unique tumour response seen with immunotherapeutic drugs. iRECIST will be used by the investigator to make treatment decisions. When clinically stable, subjects should not be discontinued until progression is confirmed by the investigator, according to the rules outlined in [Appendix 1](#). This allowance to continue treatment despite initial radiologic PD takes into account the observation that some subjects can have a transient tumour flare in the first few months after the start of immunotherapy, and then experience subsequent disease response. This data will be captured in the clinical database.

For the assessments of secondary efficacies or clinical activity of the combination therapy in terms of tumour burden and response, following parameters will be determined from CT scan results:

- Disease control rate comprising best response for CR, PR as well as stable disease (SD) lasting at least 12 weeks using RECIST 1.1

- Objective response rate based on best overall response (all time points) using RECIST modified for immune-based therapies (iRECIST)
- Disease control rate comprising best response for CR, PR as well as SD lasting at least 12 weeks using iRECIST
- Duration of response
- PFS
- Overall survival rate 6 months

Exploratory efficacy: Immune cell profile of the TME in injected and noninjected lesions and genomic analysis of the TME will be done on tumour biopsy samples. See Section 8.8 for further details.

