8.3.1 Time Period and Frequency for Collecting AE and SAE Information

- All AEs or ECIs (Events of Clinical Interest) from the time of treatment start through 30 days following cessation of study treatment must be reported by the investigator. All AEs will be collected at the time points specified in the SoA (Section 1.3).
- All AEs meeting serious criteria, from the time of treatment start through 90 days following cessation of study treatment, or 30 days following cessation of study treatment if the participant initiates new anticancer therapy, whichever is earlier must be reported by the investigator. All SAEs will be collected at the time points specified in the SoA (Section 1.3).
- All pregnancies and exposure during breastfeeding, from the time of treatment/ allocation through 120 days following cessation of study treatment, or 30 days following cessation of study treatment if the participant initiates new anticancer therapy must be reported by the investigator.

Medical occurrences that begin before the start of study treatment but after obtaining informed consent will be recorded on the medical history/Current Medical Conditions section of the ECRF, not the AE section.

All SAEs will be recorded and reported to the Sponsor or designee within 24 hours, as indicated in [Appendix 4](#). The investigator will submit any updated SAE data to the Sponsor within 24 hours of it being available.

Investigators are not obligated to actively seek AE or SAE after conclusion of the study participation. However, if the investigator learns of any SAE, including a death, at any time after a subject has been discharged from the study, and he/she considers the event to be reasonably related to the study treatment or study participation, the investigator must promptly notify the Sponsor.

The method of recording, evaluating, and assessing causality of AE and SAE and the procedures for completing and transmitting SAE reports are provided in [Appendix 4](#).

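### Six-month overall survival is a secondary endpoint, but no contact is scheduled to establish who is alive at six months

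*Combined protocol and SAP*

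**What the plan says.** Section 1.1 lists "Efficacy: overall survival rate at 6 months" among the secondary endpoints, and Section 8.1 repeats it. Table 8 (Section 9.3.1) measures survival from first dose and censors subjects with no recorded death when last known alive. It then states: "The proportion of subjects who survived for at least 6 months will be provided along with 95% CI". It does not say whether this proportion is a Kaplan-Meier estimate or a crude one. Section 9.3.4 rules out imputation.

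Follow-up is tied to treatment:

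- The last column of Table 1 is EOS, "28 days after last treatment". Section 4.1 agrees: "An EOS visit will be performed for all subjects at 4 weeks after last administered study treatment".
- One of the two ways to complete the study under Section 4.4 is: "Discontinued treatment and study due to confirmed disease progression and has completed the EOS visit".
- Section 8.1 bounds imaging: "Imaging should continue to be performed until disease progression is identified and confirmed by the investigator (iRECIST), the start of new anticancer treatment". Consent withdrawal and death also end it.
- Table 6 and Appendix 6 stop treatment in clinically unstable subjects at first radiologic progression, with a repeat scan only at the investigator's discretion. For the others, Section 8.1 says: "When clinically stable, subjects should not be discontinued until progression is confirmed by the investigator".
- Sections 7.1.1 and 7.2 refer to Table 1 for follow-up data, but Table 1 has no follow-up column.

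After EOS only event-reporting duties remain. Under Section 8.3.1 serious events are reportable "through 90 days following cessation of study treatment, or 30 days following cessation of study treatment if the participant initiates new anticancer therapy".

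**The concern.** A six-month survival rate needs vital status at six months. Here the last scheduled contact depends on when treatment stops, and treatment usually stops because of progression. Censoring would then fall just after the event that most raises the risk of death. Kaplan-Meier assumes that subjects censored at a given time have the same outlook as those still followed, and this censoring breaks that assumption.

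The direction of the error depends on which deaths after EOS reach the database, and the protocol does not settle this:

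- Section 8.3.1 sets the 90-day window (30 days with new therapy), ties collection to Table 1, and does not require sites to look for events once participation ends.
- Section 8.3.7 puts progression deaths on the adverse-event page, while Appendix 4 says that expected progression deaths are not serious adverse events.
- Appendix 4 also mentions deaths in a recognised follow-up period that is not defined.

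If neither deaths nor survivors are tracked after EOS, the curve is generally too high. If deaths are recorded but survivors stay censored at EOS, it is too low. A later analysis plan cannot recover status that was never collected.

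**Working it through.** **1. Figures in the plan.** The documents give no expected six-month survival, progression-free survival or post-progression survival, so there is no survival figure to reproduce.

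**2. Calendar, with no survival assumption.** Scans fall on days 42, 84 and 126 after the start (weeks 7, 13 and 19). EOS day = last-dose day + 28. Six months = 6 × 30.4375 = 182.6 days.

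| Progression found at | Last dose at that scan | Last dose at a confirmation scan 6 weeks later |
|---|---|---|
| day 42 | 42 + 28 = 70 | 42 + 42 + 28 = 112 |
| day 84 | 84 + 28 = 112 | 84 + 42 + 28 = 154 |
| day 126 | 126 + 28 = 154 | 126 + 42 + 28 = 196 |

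Five of the six paths end before day 183. Dose delays can move EOS later. Section 4.1 itself expects individual study duration to start at 2 months.

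**3. Assumed survival model.** Time to progression is exponential (rate λ), followed by exponential post-progression survival (rate μ), with no death before progression. Then S(t) = (μe^(−λt) − λe^(−μt))/(μ − λ), or (1 + λt)e^(−λt) when λ = μ. With rate = ln 2/median and t = 6 months:

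- medians 2 and 3 months: (0.2310 × 0.125 − 0.3466 × 0.25)/(0.2310 − 0.3466) = 0.50
- 2 and 6 months: 0.69
- 3 and 3 months: (1 + 1.386) × 0.25 = 0.60
- 3 and 6 months: 0.75

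**4. Simulated bias.** 400,000 subjects per cell. Progression is found at the next scan (days 42, 84, 126, 168, then every 63 days). EOS is last dose + 28 days, but not before the progression scan. Entries are Kaplan-Meier minus true six-month survival, in percentage points, across the four median pairs.

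- A: nothing tracked after EOS.
- B: deaths recorded to 90 days after the last dose, survivors censored at EOS.
- C: deaths and survivors both tracked to 90 days.

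| Last dose | A | B |
|---|---|---|
| 21 days before the progression scan | +14.0 to +22.7 | −2.2 to −9.1 |
| at the progression scan | +9.0 to +12.9 | −3.1 to −9.3 |
| 21 days after it | +5.4 to +7.4 | −3.0 to −8.1 |
| at a confirmation scan 42 days later | +3.1 to +4.1 | −2.7 to −6.7 |
| mix: 20-30% at the progression scan, the rest at confirmation | +4.0 to +6.2 | −2.7 to −7.2 |

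C gives +0.2 to +4.3 over all patterns and +0.4 to +0.8 in the mix. In A, 23-76% of subjects are censored before six months over all patterns, and 27-49% in the mix.

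**5. Sensitivity.**

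- Allowing death before progression (median 6, 12 or 24 months; last dose at the progression scan or later) changes A to −0.1 to +10.6 and B to −3.0 to −13.9. A is near zero when the death rate is the same before and after progression.
- A second set of assumptions used progression medians of 2-4 months, post-progression medians of 4-9 months, median 36 months to death without progression, and 40% unstable at first progression. It gives 40-68% censored before six months and +4 to +9 points with censoring at EOS. If all later deaths are learned of but survivors are not updated, the error is −5 to −16.
- Crude proportions do worse under this second set. Subjects seen alive at six months divided by N is 27-56 points too low. One minus observed deaths divided by N is 7-20 points too high.

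**6. At trial size.** In scenario A with 25% stopping at the progression scan, about 7-12 of 26 and 12-19 of 43 subjects are known alive at six months. With full follow-up the figures would be 13-20 and 21-32. The exact 95% interval near 50% is 30-70% for n = 26 and 33-65% for n = 43.

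**The case against.** The strongest case is that little hangs on this. The study is non-comparative, has no survival hypothesis or threshold, and does not name survival among the data that the monitoring committee weighs. The realistic bias lies mostly within one cohort's sampling error. That stands and limits the weight of the point, although a confidence interval does not cover bias.

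If sites used the 90-day window to establish status for everyone, the bias in the realistic mix would nearly vanish (+0.4 to +0.8 points). That is possible but not assured. The window covers events, shortens to 30 days with new therapy, and is tied to a schedule that ends at EOS.

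The 9-23 point errors need every subject to stop at or before the first progression scan, whereas Section 8.1 keeps clinically stable subjects on treatment until confirmation. This is right, and the mix is the better guide.

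Subjects who stop for toxicity and are scanned past EOS have their last scan, not EOS, as last contact. This also stands, but it is a small exception.

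Death and censoring dates in the subject listings would partly show, after the fact, which way the error runs. They would not supply the missing status, and the direction cannot be known in advance.

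**Conclusion.** The point holds. The protocol lists six-month survival as an endpoint and schedules no contact that would establish it for most early progressors. The calendar result needs no survival assumption, only on-schedule dosing. The size of the bias does rest on assumed survival times: in the realistic mix about 4-6 points too high with nothing tracked after EOS, or about 3-7 points too low if deaths are recorded to 90 days and survivors are not updated. Allowing deaths before progression widens these to roughly 0 to +11 and −3 to −14. Followed as written, the plan would give an unreliable six-month rate and survival curve. The damage is confined to a descriptive secondary endpoint, but it should be fixed because vital status missed during the study may not be recoverable.

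**What to change.** Add to Table 1 and Section 4.4 a vital-status check, by phone or medical record, at six months after first dose for every treated subject who has not withdrawn consent to further data. Add a status sweep of all treated subjects at data cut-off. State in Table 8 that the six-month rate is the Kaplan-Meier estimate with its 95% confidence interval from these data. With complete six-month status this equals the crude proportion, so the wording is secondary and could instead go in the analysis plan.

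The cost is a small amendment with consent wording, needing ethics committee and, when applicable, authority approval (Appendix 2), for about 15 centres in 4 countries. It means about 69 + 2 × 2 = 73 calls or record checks (69 evaluable subjects plus up to 2 replaced per cohort) and the cut-off sweep. It adds no visit, sample or scan.
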